- AEs considered related to the trial medication as judged by a medically qualified investigator and all SAEs (related and unrelated to trial medication) will be followed until resolution. Resolution is defined as the return to baseline status or stabilization of the condition when investigator deems further observations or examinations no longer required as medically indicated.
- If the event causing the withdrawal occurred between days 28 and the final study visit (follow-up visit), and the event was designated as not product-related, the study withdrawal will be recorded with no additional follow up.

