1.5.3 Safety Analysis Set

The safety analysis set will consist of all infants in whom any study drug (placebo or NTRA-2112) was initiated. If both members of a pair of twins are participating in the study, the safety analysis set will include both infants.

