2.3 SAFETY ANALYSIS

All safety analyses will be performed on the Safety Analysis Set. Safety data presented by treatment group will be summarized on an "as treated" basis. Safety variables include the extent of exposure, treatment-emergent adverse events (TEAEs), clinical laboratory parameters, vital signs, and other relevant variables. Study Day 1 for all safety analyses is defined as the date of the first dose of study drug.

Both fraternal and identical twins enrolled in the study, will be included in the safety analyses.

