2.3.2.1 Adverse Events

Adverse events (AEs) experienced by the subjects will be collected from initiation of dosing through the final study visit and will be coded using the latest version of the Medical Dictionary for Regulatory Activities (MedDRA) per the Data Management Plan.

Adverse event data will be categorized according to their onset date into the following study periods:

• Treatment-emergent adverse events are the ones that they started during or after administration of the first dose of study medication up till the last dose date + 30 days. In addition, medical history events that worsen in severity after the start of dosing will be considered treatment-emergent adverse events.

Confidential Page 30 of 40

AEs during the 3 month corrected age follow up period : < last dose date + 30 days -
 Month 3 follow-up visit

- AEs during the 12 month corrected age follow up period : < Month 3 follow-up visit <= Month 12 follow-up visit
- AEs during the 24 month corrected age follow up period : < Month 12 follow-up visit <= Month 24 follow-up visit

If an AE has a missing onset date then unless the stop date of the AE indicates otherwise, this will be considered an ongoing AE. Similarly, if an AE has a partial onset date, then unless the partial onset date or the stop date indicates otherwise, this will be considered an ongoing AE.

Only those AEs that are treatment-emergent will be included in summary tables. All AEs, treatment-emergent or otherwise, will be presented in subject data listings.

TEAEs will be summarized by treatment group, separately for the four reporting periods above. The incidence of TEAEs will be reported as the number (percent) of subjects with TEAEs within SOC and PT. Subjects will be counted only once within a SOC and PT, even if the subject experienced more than one TEAE within a specific SOC and PT. The number (percent) of subjects with TEAEs will also be summarized by maximum severity of Common Terminology Criteria for Adverse Events (CTCAE) and the relationship to the study drug (unlikely, possible, probable).

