2.3.2.2 Deaths, Serious and Other Significant Adverse Events

The number (percent) of subjects with TEAEs leading to death will be summarized by MedDRA SOC and PT for each treatment group separately for the on-study period and the long-term follow-up period. A subject data listing of all AEs leading to death will be provided.

The number (percent) of subjects with treatment-emergent serious adverse events (SAEs) will be summarized by MedDRA SOC and PT for each treatment group, separately for the on-study period and the long-term follow-up period. A subject data listing of all SAEs will be provided.

The number (percent) of subjects with TEAEs leading to discontinuation from study treatment will be summarized by MedDRA SOC and PT for each treatment group during the on-study period. A subject data listing of all AEs leading to discontinuation from study treatment will be provided.

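### Follow-up AE percentages default to all infants ever dosed, so infants withdrawn or lost before a period count as event-free in it; the SAP also contradicts itself on which AEs enter those tables

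*SAP*

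**What the plan says.** SAP 2.3.2.1 divides adverse events into four successive periods: first dose to last dose plus 30 days, then to the 3-month, 12-month and 24-month visits. It states: "TEAEs will be summarized by treatment group, separately for the four reporting periods above". The statistic is a crude count and percentage: "The incidence of TEAEs will be reported as the number (percent) of subjects with TEAEs within SOC and PT". SAP 2.3.2.2 treats fatal AEs and SAEs in the same way, "separately for the on-study period and the long-term follow-up period".

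Neither section names a denominator. The general rule in SAP 2.3 is "All safety analyses will be performed on the Safety Analysis Set", and SAP 1.5.3 defines that set: "The safety analysis set will consist of all infants in whom any study drug (placebo or NTRA-2112) was initiated". Being alive or still followed at a later date is not a condition.

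SAP 2.3.2.1 also limits what can appear in the tables. Treatment-emergent AEs are those that "started during or after administration of the first dose of study medication up till the last dose date + 30 days", plus medical-history conditions that worsen after dosing starts. It adds: "Only those AEs that are treatment-emergent will be included in summary tables".

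On follow-up, Protocol 9.5.1 says of a withdrawal after day 28 for an event judged unrelated to the product that "the study withdrawal will be recorded with no additional follow up". The disposition summary in SAP 2.1.1 covers completion of treatment and of the 3-month visit, but not of the 12- or 24-month visits.

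**The concern.** A percentage for a follow-up period can be read as a risk only if the infants in its denominator could have had an event recorded in that period. An infant who withdrew or was lost before the period began cannot add to the numerator. If that infant stays in the denominator, missing information is counted as absence of an event.

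Two consequences follow. Any loss lowers the later-period percentages. If one arm loses more infants than another, its percentage falls further and it looks safer than it is. A reader could not correct for this from the planned output, because 12- and 24-month retention by arm is not among the planned summaries.

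The follow-up tables matter because Protocol 12.2.4 wants AEs and SAEs from the whole trial, follow-up included, to be summarized, and Protocol 15.6 leaves open a possible long-term effect on insulin antibodies.

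**Working it through.** **Step 1. Is there a denominator other than all treated infants?** The sections line up as follows.

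| Place | What it fixes |
|---|---|
| SAP 2.3 | Population for all safety analyses: Safety Analysis Set |
| SAP 1.5.3 | That set: every infant dosed, both twins |
| SAP 2.3.2.1 | Number (percent) by period; no period-specific N, no person-time |
| SAP 2.3.2.2 | Number (percent) in long-term follow-up; no period-specific N |
| SAP 2.3.2 | All available data used; nothing imputed |

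Elsewhere the SAP does restrict a denominator: the vital-sign shift tables in 2.3.4.1 take only infants with both baseline and later data. For AEs it gives no such rule, so all treated infants is the default.

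**Step 2. Which events would the later tables hold?** Read literally, SAP 2.3.2.1 closes the treatment-emergent window at last dose plus 30 days and admits only treatment-emergent events to tables. The 3-, 12- and 24-month TEAE tables that it requests would then be nearly empty; worsened medical history is the only category without a stated end. SAP 2.3.2.2 likewise limits its summaries to treatment-emergent events. The denominator matters only once post-treatment events are admitted.

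**Step 3. The plan's own figures on loss.** The AE sections state none. The only explicit rate is the 5% dropout in SAP 3.1, and it reproduces: 144 / 0.95 = 151.6, so 152 per arm. SAP 1.3.3 raises 115 to 130 for missing data, an implied allowance of 15 / 130 = 11.5%. Both concern the primary endpoint, observed within 28 days. Neither is a 12- or 24-month loss rate.

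**Step 4. Size of the understatement.** Let p be the period risk among infants still followed, assumed equal in those lost, and l the share of treated infants lost before the period.

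Reported percent = p × (1 − l). With p = 20% (assumed):

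| Loss l (assumed) | Reported |
|---|---|
| 5% | 20 × 0.95 = 19.0% |
| 10% | 20 × 0.90 = 18.0% |
| 20% | 20 × 0.80 = 16.0% |
| 25% | 20 × 0.75 = 15.0% |

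The relative shortfall equals l whatever the value of p.

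**Step 5. Comparison between arms.** The reported risk ratio is the true ratio × (1 − l on active) / (1 − l on placebo).

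| Loss active / placebo (assumed) | True ratio 1.00 is shown as |
|---|---|
| 10% / 10% | 1.00 |
| 20% / 10% | 0.80 / 0.90 = 0.89 |
| 25% / 10% | 0.75 / 0.90 = 0.83 |
| 10% / 20% | 0.90 / 0.80 = 1.125 |

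With a true 30% against 20% (ratio 1.50), 25% loss on active and 10% on placebo would show 22.5% against 18.0%, a ratio of 1.25. With equal loss the ratio is correct, though both percentages are low.

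**The case against.** **The denominator is a default, not an explicit choice.** SAP 2.3 names a population, and a table drawn from it could still show the number in follow-up. This stands. A reader might infer that the sponsor decided to count lost infants as event-free; the documents show only that nothing else is specified.

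**Deaths.** For infants who died, events over all treated infants is a valid absolute risk with death as a competing event. It is not understated. This stands, and it confines the bias argument to infants withdrawn or lost.

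**Retention efforts.** Protocol 9.5.1 keeps infants withdrawn for an event in the first 28 days under follow-up to 24 months if consent remains, encourages withdrawing families to return for safety visits, and follows related AEs and all SAEs to resolution. Protocol 13.1 requires efforts to reach those lost. These provisions reduce loss. They do not remove it, and following an existing event to resolution does not detect a new one in a later period.

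**Arm distortion and its size.** A reader might infer that the follow-up comparison is biased in favour of the drug, or that loss will be at least 11.5%. The documents support neither: they give no long-term loss rate and no evidence that loss will differ by arm.

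**Purpose of follow-up.** A reader might take long-term safety to be the declared reason for the 24-month visits. The safety objectives in both documents do not say so; Protocol 15.6 raises possible long-term effects without tying them to those visits.

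**Limited consequence.** Protocol 12.4.4 makes the safety analysis descriptive, all AEs are listed, and Protocol 12.4.2 lists dropouts with reason and time. True, but a percentage in a table will be read as a risk, and rebuilding denominators from listings should not be left to the reader.

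**Conclusion.** The point holds in a limited form. By default, the plan counts infants withdrawn or lost before a follow-up period as event-free in it. Later-period percentages are then too low by about the share lost: at an assumed 5% to 25%, a true 20% appears as 19% to 15%. The ratio between arms is affected only if loss is unequal, and nothing in the documents establishes that it will be. The calculation assumes that infants lost have the same risk as those followed and that loss occurs before the period starts. It does not apply to infants who died.

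The contradiction over treatment-emergent events comes first, because on the literal text there is little in the later tables for any denominator to act on. The remedy is inexpensive and changes what the follow-up tables can show, so it should be made, but it does not touch the efficacy conclusions.

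**What to change.** 1. In SAP 2.3.2.1, keep treatment-emergent AEs up to last dose plus 30 days and define post-treatment AEs as a separate category that is also tabulated. Carry the same split into 2.3.2.2 for SAEs and deaths.
2. For each period after last dose plus 30 days, show by arm the number of infants alive and in follow-up at its start. Periods are bounded by actual visits, so state the boundary for an infant who misses one.
3. Report the percent on that number, and events per infant-month with time ending at death, withdrawal or last contact. The rate also handles loss within a period.
4. Keep the percent of all treated infants beside these, as the absolute risk with death as a competing event. For the treatment-emergent period, the full Safety Analysis Set remains the denominator.
5. Extend SAP 2.1.1 to 12- and 24-month retention and deaths by arm.

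The cost is SAP wording and revised table shells; it needs only dates already recorded. There are two drawbacks. Each period has its own N. The at-risk percent conditions on survival and retention after randomisation, so the infants compared may no longer be balanced as randomised; it should be read beside the all-treated percent, not instead of it.

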2.3.2.2 Deaths, Serious and Other Significant Adverse Events

The number (percent) of subjects with TEAEs leading to death will be summarized by MedDRA SOC and PT for each treatment group separately for the on-study period and the long-term follow-up period. A subject data listing of all AEs leading to death will be provided.

The number (percent) of subjects with treatment-emergent serious adverse events (SAEs) will be summarized by MedDRA SOC and PT for each treatment group, separately for the on-study period and the long-term follow-up period. A subject data listing of all SAEs will be provided.

The number (percent) of subjects with TEAEs leading to discontinuation from study treatment will be summarized by MedDRA SOC and PT for each treatment group during the on-study period. A subject data listing of all AEs leading to discontinuation from study treatment will be provided.

2.3.3 Clinical Laboratory Parameters

In summaries, figures, and listings, lab results and normal ranges will be presented in International System (SI) units.

Confidential Page 31 of 40

2.3.3.1 Blood Chemistry

For the purposes of clinical chemistry shift tables, baseline will be defined as the assessment prior to randomization and maximum or minimum value post-baseline will be calculated over the entire study period, up to the 3-month follow-up visit.

Changes in blood chemistry variables between baseline and post-baseline assessments will be calculated. The change from baseline is defined as the post-baseline visit value minus the baseline visit value. There will be no imputation for missing values. For values recorded with a leading greater than or less than symbol (">", "<"), the reported numeric value will be used for analysis and the value with the symbol will be included in the listings, unless otherwise specified. For example, a value of <0.01 will be analyzed as 0.01 and listed as <0.01.

Absolute values will be compared to the reference range and classified as normal, abnormal, or not performed. The abnormal values will be further classified as clinically significant or not clinically significant.

Data for subjects who have treatment-emergent changes outside laboratory reference ranges will be presented. This data presentation will include all visits for this subset of subjects.

Maximum post-baseline ALT and AST will be presented, expressed as multiples of ULN. AST and ALT will be presented in multiples of the following ULN \le 1, >1-3, >3-5, >5-10, >10.

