SAFETY OBJECTIVES	To compare the safety of 2 doses of NTRA-2112 to placebo in preterm infants.	
STUDY DESIGN	Multi-center, double-blind, randomized, three-arm, parallel-group, placebo-controlled.	
STUDY ARMS	Treatment A: NTRA-2112 TREATMENT A, 0.04 IU/g to obtain 400 μU/ml daily enteral intake administered with preterm infants' nutrition Treatment B: NTRA-2112 TREATMENT B, 0.2 IU/g to obtain 2000 μU/ml daily enteral intake administered with preterm infants' nutrition Treatment C: Placebo oral formulation administered with preterm infants' nutrition	
DURATION OF TREATMENT	Up to 28 treatment days or discharge from the hospital, whichever occurs first.	
DURATION OF FOLLOW-UP	24 months corrected age. Duration would be dependent on the gestational age at birth of the infant.	
STUDY POPULATION	Pre-term infants 26-32 weeks gestation and birth weight ≥ 500g, up to day 5 of life	

INCLUSION CRITERIA

- Male or female pre-term infant 26 and up to 32 weeks gestation (32 weeks + 0 day maximum). Gestational age matching (±2 weeks) between maternal dates and/or early antenatal ultrasound
- 2. Birth weight ≥ 500g
- 3. Singleton or twin birth
- 4. Postnatal age up through and including Day 5 (up to 120 hours post birth)
- 5. Fraction of inspired oxygen ≤ 0.60 at enrolment
- Subjects must demonstrate cardiovascular stability at time of enrolment and would be considered unstable if they require >40% oxygen with blood pressure support and the need for umbilical artery cauterization
- 7. Infant is able to tolerate enteral feed
- 8. Infant is expected to wean off parenteral nutrition (PN) at the primary hospital
- 9. Informed consent form signed by parents or legal guardian
- In the Investigator's opinion, the infant is able to comply with the study procedures and sufficiently stable to partake in the trial to completion
- * If both exist and difference > 2 weeks, based on early antenatal ultrasound

EXCLUSION CRITERIA

- 1. Complete enteral feeding
- Major congenital malformation (e.g., infants with genetic, metabolic, and/or endocrine disorder diagnosed before enrolment)
- 3. High index of suspicion of infection before enrolment**
- Intra-uterine growth retardation (IUGR) defined as either weight for gestational age less than the third percentile or less than the 10th percentile with Doppler abnormalities in utero ***.
- 5. Confirmed necrotizing enterocolitis (NEC)

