1.3 SUMMARY OF THE STUDY DESIGN

1.3.1 General Study Design and Plan

[figure not shown]
The study is a multi-center, double-blind, randomized, three-arm, parallel-group, placebo-controlled study to assess the efficacy and safety of NTRA-2112.

Infants will be enrolled within 5 days from birth (at least 6 hours post birth and up to 120 hours post birth) and will be treated for 28 days or until hospital discharge (whichever comes first). The study also includes a follow-up period up to 24 months corrected age.

Full enteral feeding is defined as reaching 3 consecutive days in which the infant consumed at least 150 ml/kg/day of enteral nutrition.

Enrolled infants will be under supervision at a NICU.

[figure not shown]
Figure 1: Study Flow Diagram

Confidential Page 12 of 40

Statistical Analysis Plan V1.3 SAP Date: 06APR2018

Protocol No: FIT-04 Protocol Version: 7.0

Confidential Page 13 of 40

Statistical Analysis Plan V1.3 SAP Date: 06APR2018

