1.3.2 Randomization and Blinding

Following screening procedures eligible infants will be randomly assigned to one of the three treatment groups in a 1:1:1 ratio. Randomization, stratified by the gestation age group, should take place as close as possible to treatment initiation and within 24 hours of confirmation of eligibility.

Treatment should commence at postnatal age of up to and including Day 5 (up to 120 hours post birth).

Commencement of the treatment period for infants who are fed solely on own mother's milk should not begin within the first 72 hours post birth.

Randomization will be performed using random allocation generated by computer code. If both members of the twin pair are eligible to be included in the study at the same time, the firstborn will be randomized and the other sibling will be automatically allocated to the same treatment group as the firstborn sibling.

If siblings are determined to be eligible for the study at different times, the sibling who is determined to be eligible for the study first will be randomized first (regardless of birth order), and the other sibling will be automatically allocated to the same treatment group. The assigned medication numbers (kit number) will be entered in the electronic case report form (eCRF), and the corresponding medication kit administered to the infant.

It is assumed that in all cases when twins are both in the study, the first born will be the first one entered, and therefore the one who is randomized. However, to avoid ambiguity, any reference in this SAP to "first born" is intended to mean the first entered (and therefore randomized) into the study. Similarly, reference to "second born" is intended to mean the second twin entered (and who, therefore, is not randomized, but follows the treatment assignment of the twin who was first entered).

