1.6.4 Analysis Visit Windows for Follow-up Visits

For follow-up endpoints at 3, 12 and 24 months, the variables will be summarized based on the closest scheduled visit for that variable based on "analysis-defined visit windows." These visit windows have been constructed so that every observation collected can be allocated to a unique visit. No visit windows will be defined for the screening visit.

The analysis-defined visit windows for assessments conducted at 3-month, 12-month, and 24-month are summarized in Table 2.

Table 2: Analysis - Defin	ned Visit windows f	for measurements rec	orded for follow-ur	o visits

Follow-up Visit	Scheduled Study Day	Maximum Windows
3-month	3-month corrected age	Day after the discharge until
		7.5-month of corrected age
12-month	12-month corrected age	7.5-month + 1 day until 18-
		month of corrected age
24 -month	24-month corrected age	18-month + 1 day until 30-
	_	month corrected age

Note: 7.5-month is the mid-point between 3-month and 12-month, and 18-month is the mid-point between 12-month and 24-month. The exact mid-point will be determined as the day which has equal distance from two adjacent visits if there are odd number of days in between, or it is the earlier visit pluses a half number of days if there are event number of days in between,

If multiple readings are recorded within a single analysis-defined visit window, the following rules will apply:

- If there are 2 or more valid, non-missing observations within the same visit window, then the non-missing one closest to the scheduled visit day will be used in the analysis.
- If 2 valid observations are equidistant from the scheduled visit, then the non-missing observation with the earlier collection date will be used in the analysis.

Confidential Page 17 of 40

• If 2 or more valid observations are collected on the same day, then the non-missing observation with the earlier collection time will be included in the analysis.

If a visit window does not contain any observations, then the data will remain missing.

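### The chemistry worst-value tables pool on-treatment values with values up to the 3-month visit, months past the SAP's treatment-emergent window, and should be split by period

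*SAP*

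**What the plan says.** SAP 2.3.3.1 builds the chemistry shift tables from a baseline before randomization and one extreme per infant: the "maximum or minimum value post-baseline will be calculated over the entire study period, up to the 3-month follow-up visit". It also tabulates the maximum post-baseline ALT and AST as multiples of the upper limit of normal, with no separate window. It promises a display of infants with treatment-emergent changes outside the reference range, but does not define that term for laboratory data. SAP 2.3.2 adds that safety analyses use unscheduled and repeat measurements.

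For adverse events the SAP does set a window. Under 2.3.2.1 an event is treatment-emergent if it starts "during or after administration of the first dose of study medication up till the last dose date + 30 days", and three follow-up periods come after that: "TEAEs will be summarized by treatment group, separately for the four reporting periods above". Deaths and SAEs (2.3.2.2) are split into an on-study and a long-term period. Descriptive glucose summaries (2.3.3.2) cover Days 1 to 28 and the 3-month visit.

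The Protocol synopsis gives treatment duration as "Up to 28 treatment days or discharge from the hospital, whichever occurs first". SAP 1.6.4, Table 2, lets an observation count towards the 3-month visit from the day after discharge until "7.5-month of corrected age".

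**The concern.** The worst-value rule merges an exposure of at most four weeks with a follow-up several times as long. An infant with normal chemistry throughout dosing, and one abnormal result from a later illness, is counted in the same cell as an infant whose ALT rose during dosing. If late abnormalities occur at a similar rate in every arm, they add a common background and narrow any difference between arms. The table also cannot show whether a shift arose during exposure or months later.

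A second point concerns programming. The laboratory text speaks of treatment-emergent changes, while the SAP's only dated definition of treatment-emergent is the adverse-event one. A programmer has to choose between last dose + 30 days and the 3-month visit. A chemistry abnormality and the adverse event recorded for it could then be assigned to periods under different rules.

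**Working it through.** **The plan's own figure.** The Table 2 limit is the mid-point of the 3- and 12-month visits: (3 + 12)/2 = 7.5 months. It reproduces.

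**Interval from last dose to the 3-month visit.** The documents do not state it, so it is derived here.

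Inputs:
- Gestational age at birth 26+0 to 32+0 weeks (Protocol 8.2); term taken as 40 weeks for corrected age (Protocol 3).
- First dose by 120 hours of age (SAP 1.3.2). The earliest is taken as 6 hours, from the enrolment window, "at least 6 hours post birth and up to 120 hours post birth" (SAP 1.3.1).
- Full 28-day course, so last dose age = first dose age + 27 days = 27.25 to 32 days.
- One month = 30.44 days, so 3 months = 91.3 days and 7.5 months = 228.3 days.

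Formula: gap = (40 − GA) × 7 + corrected age in days − last dose age.

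| GA at birth | Nominal 3-month visit | At the 7.5-month limit |
|---|---|---|
| 26+0 | 98 + 91.3 − (27.25 to 32) = 162 to 157 days (5.3 to 5.2 months) | 98 + 228.3 − (27.25 to 32) = 299 to 294 days (9.8 to 9.7 months) |
| 32+0 | 56 + 91.3 − (27.25 to 32) = 120 to 115 days (3.9 to 3.8 months) | 56 + 228.3 − (27.25 to 32) = 257 to 252 days (8.4 to 8.3 months) |

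The nominal range is thus 115 to 162 days, and the range at the limit is 252 to 299 days. After a full course the treatment-emergent window closes at Study Day 28 + 30 = 58. Taking 30 days from the nominal gaps leaves 85 to 132 days (2.8 to 4.3 months) that count towards the chemistry extreme but lie outside that window.

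**Possible effect on the contrast.** The documents give no abnormality rates, so every rate here is an assumption. Let p be the on-treatment rate in an arm and q a late rate, equal across arms and independent of p. Then P(ever abnormal) = 1 − (1 − p)(1 − q), and the risk difference is multiplied by (1 − q). With p = 20% v 10%:

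| Late rate q | Ever abnormal | Risk difference (points) | Risk ratio |
|---|---|---|---|
| 0% | 20.0% v 10.0% | 10.0 | 2.00 |
| 2% | 21.6% v 11.8% | 9.8 | 1.83 |
| 5% | 24.0% v 14.5% | 9.5 | 1.66 |
| 10% | 28.0% v 19.0% | 9.0 | 1.47 |
| 20% | 36.0% v 28.0% | 8.0 | 1.29 |

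The ratio depends on the assumed starting rates. With 15% v 5% it falls from 3.00 to 2.42 at q = 2% and to 1.33 at q = 20%. With 25% v 10% it falls from 2.50 to 2.25 and 1.43.

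**The case against.** The SAP states its window openly, and that window matches the data cut: SAP section 2 places the primary analysis after the last 3-month visit, using all data to that point. A later value can only make an infant's maximum or minimum more extreme, so a reader who infers that on-treatment signals are lost goes beyond the text. It would also go too far to call the late values unrelated to the product, since a delayed effect is possible. These objections stand.

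Other outputs partly separate the periods. SAP 2.3.2 calculates change from baseline at each scheduled time point, and 2.3.3.1 shows all visits for infants with treatment-emergent out-of-range changes. That help is partial. Unscheduled peaks do not belong to a scheduled time point, the all-visit display depends on the term left undefined for laboratory data, and neither output is stated to give on-treatment shift counts by arm.

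Protocol 11.3 defines treatment-emergent by comparison with screening, with no end date, and the SAP has later adverse-event periods, so late events are not ignored. This is correct. The mismatch lies between the SAP's own dated window and its chemistry rule, and no result goes unreported.

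On timing, a reader might take the visit itself to fall anywhere from 4 to 10 months after dosing. The documents do not support that. The upper figure is the limit of an analysis window that opens the day after discharge and favours the observation closest to schedule.

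Finally, safety analyses are descriptive (Protocol 12.4.4), and the chemistry sampling schedule is not in the public text, so the number of late samples per infant is unknown. Both facts limit the weight of the point.

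**Conclusion.** The point holds as a minor safety-reporting issue. The chemistry extremes pool data from at most 28 days of dosing with data up to a visit nominally 3.8 to 5.3 months after the last dose of a full course, and up to 9.8 months at the Table 2 limit. Elsewhere the SAP reports adverse events, SAEs and descriptive glucose summaries by period. Late values can create shifts in infants who were normal on treatment, and the resulting tables cannot date a shift.

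Loss of contrast is possible but not established. Its size rests on an assumed late rate that is equal across arms and independent of on-treatment status. At a 2% late rate it is slight (risk ratio 1.83 against 2.00), and at 20% it is considerable (1.29). The timing assumes a full course. If dosing stopped on Day 1 in an infant born at 26+0 weeks, the gaps would be 6.2 months nominally and 10.7 months at the limit.

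A reader might also conclude that the tables should simply end at last dose + 30 days. That does not follow. Discharge and unscheduled values between that date and the 3-month visit would then drop out of every worst-value summary, and the SAP itself allows up to 180 days to observe discharge (section 4).

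**What to change.** In SAP 2.3.3.1, present the worst-value shift tables and the ALT/AST multiples-of-ULN table in three columns per arm:

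- (a) first dose to last dose + 30 days;
- (b) after that date through the 3-month visit, including discharge and unscheduled values;
- (c) overall, as now planned.

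State that window (a) also defines treatment-emergent for laboratory changes.

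The cost is a few lines of SAP text and the extra table columns. No value is dropped, and no hypothesis test or sample size changes.
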